9. REGULATORY CONSIDERATIONS

9.1 Institutional Review of Protocol

The protocol, the proposed informed consent and all forms of participant information related to the study (eg, advertisements used to recruit participants) will be reviewed and approved by the Stanford IRB. Any changes made to the protocol will be submitted as a modification and will be approved by the IRB prior to implementation. The Protocol Director will disseminate the protocol amendment information to all participating investigators.

9.2 Data Management Plan

The study charts will be stored in a locked office in the Cancer Clinical Trials Office. Demographic information will be kept using OnCore.

During the clinical investigation, the Protocol Director will evaluate the progress of the trial, including periodic assessments of data quality and timeliness, participant recruitment, accrual and retention, participant risk versus benefit, performance of trial sites, and other factors that can affect study outcome.

The Stanford Cancer Institute Data and Safety Monitoring Committee (DSMC) will audit study related activities to determine whether the study has been conducted in accordance with the protocol, local standard operating procedures, FDA regulations, and Good Clinical Practice (GCP). This may include review of regulatory binders, case report forms, eligibility checklists, and source documents. In addition, the DSMC will regularly review serious adverse events and protocol deviations associated with the research to ensure the protection of human subjects. Results of DSMC audits will be communicated to the IRB and the appropriate regulatory authorities at the time of continuing review, or in an expedited fashion, as needed.

10. Statistical Considerations and Evaluation of Results

10.1 Study Endpoints

Primary endpoint:

- Number of participants with successful PET-based detection of ER-positive breast cancer and metastases

Other endpoints:

None

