2.4.2 Endpoints

Primary Endpoints

- Number of lesions identified on ^{68}Ga -RM2 PET/MRI
- Correlation of ^{68}Ga -RM2 uptake and ER positivity on biopsy (when done as clinically indicated)

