2.4.3 ClinicalTrials.gov Outcomes

Primary Outcome

Title: Number of lesions identified on ^{68}Ga -RM2 PET/MRI

Description: Findings deemed as compatible with breast cancer

The outcome will be reported as the number of participants with successful PET-based detection of ER-positive breast cancer and metastases

Timeframe: 12 months

Safety outcome: No

Secondary Outcome

None

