10.2. Accrual estimates

We anticipate enrolling 20 patients in total.

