10.3 Analyses Plans

As this is an initial feasibility pilot, and we have no control over the biopsy process, we will only estimate the per-lesion sensitivity of ^{68}Ga -RM2 PET-based in detecting the known ER+ lesions.

There will be at least 20 ER+ lesions, and we expect that the PET sensitivity will be at least 80%. A sample of 20 will provide 90% power at one-sided 5% error to demonstrate that a sensitivity of 80% is greater than chance performance. A sample of 25 will provide 80% power to demonstrate sensitivity of 75%, which we believe is the minimum that would justify further study.

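### Sections 2.4.2, 2.4.3, 10.1 and 10.3 do not name the same primary endpoint, and no section says how lesion calls make a participant a success

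*Combined protocol and SAP*

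**What the plan says.** - **Section 10.1** has a single primary endpoint at participant level, "Number of participants with successful PET-based detection of ER-positive breast cancer and metastases", and lists no other endpoints.
- **Section 10.3** says "we will only estimate the per-lesion sensitivity of" the PET for known ER+ lesions. It states "There will be at least 20 ER+ lesions" and expects sensitivity of at least 80%. It claims 90% power with a sample of 20, one-sided 5%, against chance performance. It adds "A sample of 25 will provide 80% power to demonstrate sensitivity of 75" per cent, and treats 75% as the least that would warrant continuing.
- **Section 10.2** fixes the number of participants: "We anticipate enrolling 20 patients in total".
- **Section 2.4.2** lists two primary endpoints. One is "Number of lesions identified on ^{68}Ga -RM2 PET/MRI". The other is the correlation of "uptake and ER positivity on biopsy (when done as clinically indicated").
- **Section 2.4.3** has a lesion-level title and the description "Findings deemed as compatible with breast cancer", but its reporting line is the participant count of section 10.1. It lists no secondary outcome.
- **Section 5.3** provides a blinded consensus read of each scan, with every lesion tabulated.
- **Section 6.3** provides 12 months of chart review for standard-of-care biopsies, and allows investigators to help choose biopsy targets from the PET findings.

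**The concern.** A team following section 10.1 would report a count of participants. Following section 10.3 it would report a lesion proportion, and following section 2.4.2 a lesion total and a correlation. All would come from the same 20 scans, and the plan does not say which is the headline result.

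The participant count has a further gap. Whether a single lesion is positive is covered by a reader's judgement and a consensus read. Whether a participant is a success is not: it could need any known lesion, all of them, or the primary and the metastases separately. The objective covers metastases and section 3.1 admits suspected recurrence, so participants with several known lesions are foreseeable. For them the rule could be chosen after the reads.

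The power figures and the 75% minimum are stated for sensitivity. They transfer to the participant count only under a condition that the plan does not impose.

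**Working it through.** **1. Endpoints side by side**

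| Section | Primary quantity | Unit | Analysis given |
|---|---|---|---|
| 2.4.2 | Number of lesions identified | Lesion | None |
| 2.4.2 | Uptake-ER correlation | Biopsied lesion | None |
| 2.4.3 | Lesion title, participant reporting line | Mixed | None |
| 10.1 | Participants with successful detection | Participant | None |
| 10.3 | Sensitivity for known ER+ lesions | Lesion | Estimate, power, 75% minimum |

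The correlation does not appear in sections 2.4.3, 10.1 or 10.3. The sample of 25 in section 10.3 exceeds the 20 participants in section 10.2, which supports reading its unit as the lesion.

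**2. The plan's power figures**

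Inputs from section 10.3: n = 20, p1 = 0.80, one-sided 5%; and n = 25, p1 = 0.75, with error and null not restated and taken as the same. Assumptions: chance means p0 = 0.50, and units are independent.

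Normal approximation: power = Φ([(p1 − p0)√n − 1.645·√(p0·q0)] / √(p1·q1)).

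- n = 20: (0.30 × 4.472 − 0.8225)/0.40 = 1.298, so 90.3%. This reproduces the stated 90%.
- n = 25: (0.25 × 5 − 0.8225)/0.433 = 0.987, so 83.8%, against the stated 80%.

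Exact binomial:

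| Units | True sensitivity | Cut-off | True error | Power |
|---|---|---|---|---|
| 20 | 80% | 15 | 2.1% | 80.4% |
| 20 | 80% | 14 | 5.8% | 91.3% |
| 25 | 75% | 18 | 2.2% | 72.7% |
| 25 | 75% | 17 | 5.4% | 85.1% |

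The normal-approximation cut-offs are 10 + 1.645√5 = 13.7 and 12.5 + 1.645 × 2.5 = 16.6, that is 14 of 20 and 17 of 25. Both exceed 5% true error. Under these assumptions no simple cut-off on 20 units gives both 90% power and at most 5% error.

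**3. How much the missing rule matters**

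Take a participant with two known lesions, per-lesion sensitivity p and within-patient correlation ρ of the calls:

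- all detected = p² + ρ·p·q
- any detected = 2p − p² − ρ·p·q
- gap = 2·p·q·(1 − ρ), which at p = 0.80 is 0.32(1 − ρ)

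| ρ (assumed) | Any | All | Gap |
|---|---|---|---|
| 0 | 0.96 | 0.64 | 0.32 |
| 0.5 | 0.88 | 0.72 | 0.16 |
| 1 | 0.80 | 0.80 | 0 |

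The gap is the shift in the expected count per such participant. With one known lesion each, the rules coincide and 16 of 20 successes are expected.

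**4. Whether the lesion benchmark carries over**

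With two independent lesions, a 75% lesion sensitivity becomes 1 − 0.25² = 93.8% (any) or 0.75² = 56.3% (all). A 50% chance value becomes 75% or 25%. Neither the minimum nor the null transfers unchanged.

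Nor does the power. Suppose a rule requires detection in each category, primary and metastasis, that holds a known lesion, and keep 15 of 20 as the cut-off. If 5 of the 20 participants (assumed) have one independent known lesion in each category, power at 80% falls from 80.4% to about 66%. If 10 do, it falls to about 49%.

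**The case against.** This is a single-arm feasibility pilot. Section 10.3 aims only to estimate sensitivity, and the plan sets out no test of the participant count and no stopping rule based on it. The word *only* in section 10.3 may limit which accuracy measures are reported, without cancelling the count in section 10.1. Section 2.4.3 can be read as a chain in which lesions are identified and participants with such findings are then counted, which suggests an any-lesion rule. The sample of 20 equals the enrolment, and 20 lesions is the floor of one per participant; at that floor the lesion figures serve participants as well.

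Much of this stands. The pilot label limits the consequences, and the any-lesion reading is plausible. It is not stated, however, and it does not say what happens when a primary is seen and a known metastasis is missed. The floor is a minimum, not a design feature. Even on the mildest reading of *only*, the count has no construction rule, analysis or benchmark of its own.

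Three stronger readings are tempting, and the documents do not support them:

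- **That lesion positivity is undefined.** Sections 2.4.3 and 5.3 provide a reader-judged call by blinded consensus.
- **That the choice of rule will shift the result by 32 percentage points.** That is the extreme for two independent lesions. The plan gives no distribution of lesions per participant, so the likely effect is unknown.
- **That the 90% power is an arithmetical mistake.** It matches a normal approximation with chance at 50%, and the plan names no exact test.

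**Conclusion.** The point holds and needs correcting before the reads. Four sections disagree on the primary endpoint, the one declared in section 10.1 has no matching analysis, and the correlation in section 2.4.2 has none anywhere. That conclusion rests on the text alone.

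The size of the effect is conditional. For each participant with two known lesions, the any/all choice moves the expected count by between 0 and 0.32 at 80% sensitivity, for correlations from 1 down to 0. If everyone has one known lesion it moves nothing.

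The power question is separate and smaller. It depends on chance meaning 50% and on independent units, neither of which the plan states. A reader might also infer that the participant count must be primary because sections 10.1 and 2.4.3 report it. Section 10.3 gives its reasoning and analysis only for per-lesion sensitivity, so either choice is defensible and the sponsor should make it.

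**What to change.** Before any scan is read:

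1. **One primary endpoint.** Name it identically in sections 2.4.2, 2.4.3, 10.1 and 10.3. Label the remaining quantities secondary or exploratory, and amend the entry in section 10.1 that lists no other endpoints.
2. **If the participant count is primary,** state the success rule and the denominator. Report the proportion with a 95% Clopper-Pearson interval (16/20: 56.3% to 94.3%; 15/20: 50.9% to 91.3%). Set a participant-level benchmark for that rule, since the 75% lesion minimum carries over only with one known lesion each.
3. **If per-lesion sensitivity is primary,** change section 10.1 and the reporting line of section 2.4.3 to match, and use an interval clustered by participant.
4. **One reference list in either case.** Include lesions whose ER+ status comes from a biopsy not prompted by the PET, taken before the scan or during the 12-month chart review. Someone who is not a reader, and who does not know the reads, compiles it. Report PET-prompted biopsies descriptively.
5. **Power, separately.** State what chance means. If it is 50% with independent units, give exact power as 80.4% (20 units, 80%) and 72.7% (25 units, 75%). Alternatively, say that the 90% and 80% are normal-approximation figures whose cut-offs, 14 of 20 and 17 of 25, have true errors of 5.8% and 5.4%. Do not present any of these as participant-level power where participants have more than one known lesion.

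The cost is wording in four sections, a little analysis code and one small non-reader step; no new scans or readers are needed. The downsides are lower stated power if exact figures are used, loss of primary status for the endpoints not chosen, and possibly few countable metastases, since the team does not control biopsies.

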10.2. Accrual estimates

We anticipate enrolling 20 patients in total.

10.3 Analyses Plans

As this is an initial feasibility pilot, and we have no control over the biopsy process, we will only estimate the per-lesion sensitivity of ^{68}Ga -RM2 PET-based in detecting the known ER+ lesions.

There will be at least 20 ER+ lesions, and we expect that the PET sensitivity will be at least 80%. A sample of 20 will provide 90% power at one-sided 5% error to demonstrate that a sensitivity of 80% is greater than chance performance. A sample of 25 will provide 80% power to demonstrate sensitivity of 75%, which we believe is the minimum that would justify further study.

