^{68}Ga -labeled DOTA-4-amino-1-carboxymethyl-piperidine-D-Phe-Gln-Trp-Ala-Val-Gly-His-Sta-Leu-NH₂ (^{68}Ga -DOTA-Bombesin or ^{68}Ga -RM2, formerly also known as BAY86-7548) is a synthetic bombesin receptor antagonist, which targets gastrin-releasing peptide receptors (GRPR) (3). Stoykow and colleagues reported the use of ^{68}Ga -RM2 in 15 patients with breast cancer. A total of 13 of 18 tumors demonstrated strongly increased ^{68}Ga -RM2 uptake compared to normal breast tissue (defined as PET-positive). All PET-positive primary tumors were ER- and PR-positive (13 of /13) in contrast to only 1 of 5 PET-negative tumors. Mean SUV_{max} of ER-positive tumors was 10.6 ± 6.0 compared to 2.3 ± 1.0 in ER-negative tumors ($P = 0.016$). In a multivariate analysis including ER, PR, HER2/neu and MIB-1, only ER expression predicted ^{68}Ga -RM2 uptake (model: $r^2 = 0.55$, $p = 0.025$). Normal breast tissue showed inter- and intraindividually variable, moderate GRPR binding (SUV_{max} 2.3 ± 1.0), while physiological uptake of other organs was considerably less except pancreas. Of note, ^{68}Ga -RM2-PET/CT detected internal mammary lymph nodes with high ^{68}Ga -RM2 uptake ($n = 8$), a contralateral axillary lymph node metastasis (verified by biopsy) and bone metastases ($n = 1$; not detected by bone scan and CT). This study demonstrated that ^{68}Ga -RM2-PET/CT is a promising imaging method in ER-positive breast cancer. *In vivo* GRPR binding assessed by ^{68}Ga -RM2-PET/CT correlated with ER expression in primary tumors of untreated patients (4).

We conducted a pilot phase evaluation of ^{68}Ga -RM2 in prostate cancer patients under an RDRC-approved protocol at Stanford University. Ten men (age range: 60 to 83 year-old; mean \pm SD: 73.1 ± 6.9) with biochemical recurrence of prostate cancer (PSA range: 3.7 to 36.4; mean \pm SD: 12.5 ± 9.8) were enrolled. PET/MRI images were acquired at

42 to 51 minutes (mean \pm SD: 47.2 ± 3.2) after injection of 3.6 to 4.1 mCi (mean \pm SD: 3.7 ± 0.2) of ^{68}Ga -RM2.

Biodistribution and localization of ^{68}Ga -RM2

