5.3 Image interpretation

The PET/MRI scans will be interpreted by ABNM certified Nuclear Medicine physicians and ABR certified Radiologists. Drs [name], [name], [name] and [name] have significant clinical experience and will be blinded to the participants' medical history and the results of other imaging modalities. Consensus read will be obtained for each scan. Each lesion will be tabulated and a comparison of lesion detection by each scanner will be conducted.

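### Section 10.3 treats lesions as independent although they come from at most 20 patients; there is no effect at one lesion each, but it grows with more, or more unevenly spread, lesions per patient

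*Combined protocol and SAP*

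**What the plan says.** Section 10.3 explains that, because this is a feasibility pilot without control over biopsies, "we will only estimate the per-lesion sensitivity of" the PET scan in known ER+ lesions. It then gives the expected yield: "There will be at least 20 ER+ lesions, and we expect that the PET sensitivity will be at least 80" per cent. It claims 90% power with a sample of 20, at one-sided 5% error, to show that 80% sensitivity beats chance. It adds: "A sample of 25 will provide 80% power to demonstrate sensitivity of 75" per cent, which it calls the minimum that would justify further study. The unit of the 25 is not stated, and no test or interval is named.

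Section 10.2 fixes the number of patients: "We anticipate enrolling 20 patients in total". Section 5.3 makes the lesion the recording unit: "Each lesion will be tabulated and a comparison of lesion detection by each scanner will be conducted". The aim covers metastases, and patients with suspected recurrence are eligible (sections 1 and 3.1). Nothing caps lesions per patient or mentions within-patient correlation.

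The primary endpoint has a different unit. Section 10.1 gives it as "Number of participants with successful PET-based detection of ER-positive breast cancer and metastases", and section 2.4.3 agrees: "The outcome will be reported as the number of participants with successful PET-based detection" of disease.

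**The concern.** Lesions in one patient share receptor biology, tracer delivery, scanner session and readers, so their detection results are likely to be correlated. If they are analysed as independent, the effective sample is overstated: the interval around sensitivity is too narrow, and a test against chance rejects too often. With 20 patients, a sample of 25 lesions would have to include at least 25 − 20 = 5 lesions that share a patient with another, so if 25 means lesions the plan's own second scenario is clustered. Chart review over 12 months (section 6.3) may add further known lesions.

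At stake is the precision attached to the one figure that the plan will set beside its 75% minimum when judging whether to go on.

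**Working it through.** **Inputs.** From section 10.3: n = 20 with sensitivity 0.80, n = 25 with sensitivity 0.75, one-sided error 5%. From section 10.2: 20 patients. Assumed: chance means 0.50 in both power statements, and the same 5% error applies to the second. The ICC and the lesion layouts are also assumed, because the documents give neither.

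**Step 1: the plan's own figures.** Normal approximation: power = Φ([(p1 − p0)√n − 1.645√(p0q0)] / √(p1q1)).

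- n = 20, p1 = 0.80: (0.30 × 4.472 − 0.822) / 0.40 = 1.298, power 90.3%. The stated 90% is reproduced.
- n = 25, p1 = 0.75: (0.25 × 5 − 0.822) / 0.433 = 0.987, power 83.8%, against 80% stated.

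Both treat observations as independent. The exact binomial test gives less:

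- n = 20: the cutoff is 15/20, with error 2.1% and power 80.4%. The normal-approximation test rejects from 14/20 (z = 0.20 / 0.1118 = 1.79), where the true error is 5.8%.
- n = 25: the cutoff is 18/25, with error 2.2% and power 72.7%.

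**Step 2: design effect.** With m lesions in a patient, DE = 1 + ICC × (Σm²/Σm − 1). For 25 lesions as 15 patients with one and 5 with two: Σm²/Σm = (15 + 20)/25 = 1.40, so DE = 1.12 at ICC 0.3 and 1.20 at ICC 0.5. For 26 lesions from 16 patients (9 with one, 5 with two, 1 with three, 1 with four): (9 + 20 + 9 + 16)/26 = 2.08, so DE = 1.32 and 1.54. The driver is Σm²/Σm, so uneven spread counts as well as the average.

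**Step 3: true error and coverage of unclustered methods.** Each patient's detections are beta-binomial with parameters p(1/ICC − 1) and (1 − p)(1/ICC − 1). Convolving over patients gives the exact distribution of the total. Error is the probability, at p = 0.5, of reaching the exact-test cutoff. Coverage is the probability, at p = 0.8, that the exact binomial 95% interval contains 0.8.

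| Layout (assumed) | DE at ICC 0.3 / 0.5 | Cutoff | Error at ICC 0 / 0.3 / 0.5 | Coverage at ICC 0.3 / 0.5 |
|---|---|---|---|---|
| 20 lesions, one each | 1.00 / 1.00 | 15 | 2.1 / 2.1 / 2.1% | 98 / 98% |
| 25: 15 with 1, 5 with 2 | 1.12 / 1.20 | 18 | 2.2 / 2.8 / 3.3% | 97 / 97% |
| 25: 19 with 1, one with 6 | 1.36 / 1.60 | 18 | 2.2 / 4.2 / 5.5% | 95 / 93% |
| 26 from 16 patients, as above | 1.32 / 1.54 | 18 | 3.8 / 6.2 / 7.8% | 92 / 89% |
| 40: two each | 1.30 / 1.50 | 26 | 4.0 / 6.3 / 7.8% | 95 / 93% |
| 40: 12 with 1, 6 with 3, 2 with 5 | 1.57 / 1.95 | 26 | 4.0 / 8.3 / 10.9% | 92 / 89% |

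**Step 4: dependence on the test.** The second row looks harmless because the exact test at 25 has slack. The normal-approximation test, the one that matches the plan's 90%, rejects from 17/25 (z = 0.18 / 0.10 = 1.8). Its error in that layout is already 5.4% without clustering and becomes 6.5 / 7.2% at ICC 0.3 / 0.5. On the design-effect scale, effective n at ICC 0.5 is 25 / 1.20 = 20.8, and normal-approximation power at 75% falls from 83.8% to 76.9%.

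**The case against.** The strongest reply is that the likeliest case is the one with no effect. The analysis is limited to known ER+ lesions, each patient enters with biopsy-proven ER+ disease, and at least 20 lesions from 20 patients fits about one each. The plan will only estimate, sets no formal decision rule, and has a primary endpoint counted in participants. Every ICC and every layout with more than one lesion per patient is an assumption. At 20 or 25 thinly spread lesions, the gap between normal and exact power (90.3 against 80.4%; 83.8 against 72.7%) is larger than the clustering effect. All of this stands, and it is why the point is minor. It does not remove the gap: the layout is unknown until the data arrive, nothing caps it, and the method has to be fixed beforehand.

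A reader might infer more than the documents support, in four ways.

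- **Projecting lesion counts from the cited 15-patient study.** Section 2.1 says "A total of 13 of 18 tumors demonstrated strongly increased" uptake, and 18/15 × 20 = 24. But only 13 + 1 = 14 of those tumours are described as receptor-positive, and the other 4 cannot be known ER+ lesions. Adding the 8 + 1 + 1 = 10 nodal and bone findings gives (14 + 10)/15 × 20 = 32, but those were found by PET and biopsy is stated for only one, so they do not form a sensitivity denominator.
- **An inflated error against 75%.** The plan names 75% as a minimum of interest but does not test against it.
- **An effect confined to many lesions per patient.** The 26-lesion and two-each rows contradict this.
- **A pilot undermined by clustering.** With one lesion each nothing changes, and a count of participants is not affected.

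**Conclusion.** The gap is real and minor. Section 10.3 makes the lesion its unit, powers it as independent, and makes no provision for lesions sharing a patient. The effect ranges from none at one lesion each to a true error of about 11% and coverage of about 89% at 40 unevenly spread lesions with ICC 0.5. Moderate layouts can already miss the nominal 5% and 95%, as 26 lesions from 16 patients shows; part of the contrast with 25 lesions is that the exact test has less slack at 26. Whether 25 spread lesions are harmless depends on the test used, which the plan does not name.

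The sizes rest on an assumed ICC of 0.3 to 0.5, assumed layouts, a beta-binomial model, chance taken as 50%, and unclustered methods supplied here because the plan specifies none. That the stated 90% reproduces only for independent lesions under a normal approximation rests on none of the clustering assumptions, only on chance meaning 50%.

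**What to change.** Change section 10.3 in two places.

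1. **Interval and test.** Report per-lesion sensitivity with a small-sample patient-clustered 95% interval whenever any patient contributes more than one lesion. Base any test against chance on it, and report the distribution of lesions per patient. One suitable method is an intercept-only logistic GEE with Mancl-DeRouen variance and t on contributing patients minus 1. In 200,000 simulated trials per scenario, over layouts including those above and ICC 0 to 0.5, its error against 50% was 2.1 to 4.2% and its coverage at 80% sensitivity 95.9 to 98.5%. This interval cannot be computed if every lesion is detected. In that case report the participant-level exact interval, labelled as a different quantity: the lower limit is 0.025^(1/k), so 20/20 gives 83.2% to 100% and 16/16 gives 79.4% to 100%. With 20 single lesions this occurs in 0.8^20 = 1.2% of studies at 80% sensitivity, and in (13/14)^20 = 22.7% if sensitivity matched the cited study's 13 of 14.

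2. **Power statement.** Say that 90% at n = 20 assumes independent lesions and a normal approximation whose 14/20 cutoff has true error 5.8%, and that the exact test gives 80.4%. Say that the 80% quoted at n = 25 and 75% sensitivity is 72.7% exact. State that 25 means lesions, if it does.

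**Cost.** A few lines of standard code and wording. With one lesion each the price is almost nil: median interval width 0.39 against 0.38, and power 80.4% either way. For the 40 unevenly spread lesions at ICC 0.1 / 0.3 / 0.5 and 80% sensitivity, width is 0.29 / 0.33 / 0.38 against 0.27 unclustered, and power against 50% is 96 / 88 / 79% against 99 / 97 / 96%. Part of that apparent loss reflects the unclustered test exceeding its nominal error.

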2.4 Study Design

This is a pilot study enrolling up to 20 participants with ER+ breast cancer, either at initial diagnosis prior to surgery or at suspected recurrence. Eligible participants will undergo baseline assessments at enrollment. Study participants will receive ^{68}Ga -RM2 and undergo a PET/MRI scan. All patients will first be seen by a Stanford Cancer Institute physician and then referred if appropriate on clinical grounds to [name] or his colleagues for this study. The following steps will take place.

1. Participants will be given a copy of the consent form s/he signed.
2. Participant will be asked to drink 1 to 2 glasses of water before arrival at the clinic
3. Vital signs (heart rate, blood pressure) will be recorded
4. Participant will be injected IV with $140 \pm 20\%$ mBq of ^{68}Ga -RM2
5. Participant will void immediately prior to the scan
6. Data acquisition will begin with a dedicated scan of the breasts, followed by a vertex to mid-thighs scan. First, localizer MRI scans will be performed to define the table positions and then MR structural imaging and diffusion weighted imaging will be performed simultaneously with PET imaging. After the dedicated scan of the breasts, a whole-body combined PET/MRI acquisition will be initiated with 3 to 5 table positions at a 2 to 4 minute acquisition time per table position.
7. Vital signs (heart rate, blood pressure) will be recorded again at the completion of the study, and the patient will be dismissed.
8. Participants will be contacted at 24 to 72 hours following the scan in order to collect record any adverse events.

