3. PARTICIPANT SELECTION AND ENROLLMENT PROCEDURES

3.1 Inclusion Criteria

1. ≥ 18 years-old
2. Biopsy proven ER+ breast cancer, either at initial diagnosis prior to surgery or at suspected recurrence.
3. Able to provide written consent
4. Karnofsky performance status of ≥ 50 (or ECOG/WHO equivalent)
5. Females must be not be pregnant per urine pregnancy test

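### Section 10.3 does not secure its 20 known ER+ lesions, does not keep RM2-directed biopsies out of the sensitivity denominator, and states a power that holds only under a normal approximation

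*Combined protocol and SAP*

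**What the plan says.** Section 10.3 limits the analysis to per-lesion sensitivity in "detecting the known ER+ lesions" and asserts that "There will be at least 20 ER+ lesions". The power claim follows: "A sample of 20 will provide 90% power at one-sided 5% error", to show that "a sensitivity of 80% is greater than chance performance". Neither the test nor the numerical value of chance is given. The same section concedes that "we have no control over the biopsy process".

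Other sections bear on the count:

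- Section 2.4: "This is a pilot study enrolling up to 20 participants". The synopsis and 10.2 give 20 as the number, and 10.4 expects 10 a year for 2 years.
- Section 3.1, criterion 2, requires biopsy-proven ER+ disease, "either at initial diagnosis prior to surgery or at suspected recurrence".
- Section 2.4.2 relates uptake to "ER positivity on biopsy (when done as clinically indicated").
- Section 6.3 collects routine-care biopsy and imaging results by chart review for 12 months. It adds that the investigators will, if treating physicians ask, help pick lesions for biopsy on the basis of the RM2 scan.

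Sections 10.1 to 10.4 do not define a known ER+ lesion. They give no assumed number of lesions per participant and no rule for participants who have none.

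**The concern.** Two things are at stake.

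The first is the count. A number stated as fact supports the power claim, yet it depends on biopsies the study does not control. Criterion 2 can be read to admit someone whose original tumour was ER+ on biopsy and whose recurrence is only suspected. That person might bring no confirmed lesion to the scan.

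The second is bias, and it matters more. A lesion biopsied because RM2 showed it cannot be a false negative. If its biopsy is ER+ and it enters the denominator, it adds one to both numerator and denominator whatever the tracer's true sensitivity. Section 10.3 treats 75% sensitivity as the minimum that would justify further study, so an upward shift of several points around that value could change the conclusion.

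**Working it through.** **Inputs.** From 10.3: 20 lesions, true sensitivity 80%, one-sided 5%. Assumed: chance means 50%, because 10.3 gives no value.

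**Step 1: the plan's own figure.** Normal approximation with the null variance, p0 = 0.50, p1 = 0.80, n = 20:

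power = Φ[(p1 − p0 − 1.645·√(p0(1−p0)/n)) / √(p1(1−p1)/n)]
= Φ[(0.30 − 1.645 × 0.1118) / 0.0894]
= Φ(1.298) = 90.3%.

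The stated 90% reproduces. An exact one-sided 5% binomial test needs at least 15/20 (actual error 2.07%) and has 80.4% power. The next looser rule, 14/20, has 91.3% power, but its error is 5.77%, above the 5% claimed.

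**Step 2: power by number of lesions, at 80% sensitivity.**

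| Lesions | Exact rule | Exact error | Exact power | Normal approximation |
|---|---|---|---|---|
| 20 | ≥15 | 2.07% | 80.4% | 90.3% |
| 19 | ≥14 | 3.18% | 83.7% | 88.7% |
| 18 | ≥13 | 4.81% | 86.7% | 87.0% |
| 16 | ≥12 | 3.84% | 79.8% | 82.7% |
| 15 | ≥12 | 1.76% | 64.8% | 80.2% |
| 12 | ≥10 | 1.93% | 55.8% | 70.6% |

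Exact power moves in a saw-tooth because the critical value is a whole number. Losing one or two lesions matters little by either method.

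**Step 3: how firm is 20?** Illustration with assumed values: 20 enrolled, one lesion each, a fraction f entering at suspected recurrence, and a fraction c of those with a confirmed ER+ lesion in place. The probability that a participant contributes is q = (1 − f) + f·c.

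- f = 0.25, c = 0.9: q = 0.975, expected count 19.5, chance of all 20 = 0.975^20 = 60%.
- f = 0.5, c = 0.5: q = 0.75, expected count 15.0, chance of all 20 = 0.75^20 = 0.3%.

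Participants with more than one lesion would raise these counts. The only per-patient figure in the protocol is the earlier RM2 breast study in 2.1: 18 tumours in 15 patients, of which 13 + 1 = 14 were ER+. That series included ER-negative tumours, so it does not settle the rate here.

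**Step 4: effect of RM2-directed lesions.** Assume 5 of the 20 lesions entered because RM2 showed them, so 15 carry real information.

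- Expected estimate at a true 70%: (15 × 0.70 + 5)/20 = 15.5/20 = 77.5%.
- Chance of at least 15/20 at a true 50% with no such lesions: P(Bin(20, 0.5) ≥ 15) = 2.1%.
- With 5 such lesions, only 10 of the other 15 must be positive: P(Bin(15, 0.5) ≥ 10) = 4944/32768 = 15.1%.

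**The case against.** A reader might infer that all 20 participants must each supply a lesion, so that 20 is a ceiling. The documents do not support that. The analysis is per lesion, the aim includes metastases, and the 25-lesion scenario in 10.3 set beside 20 participants implies 25/20 = 1.25 lesions each. Participants with several lesions can offset those with none. Correlation between lesions in one participant is a separate question.

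A reader might also infer that eligibility plainly admits people with no confirmed lesion. Criterion 2 can equally mean that the biopsy proof is obtained at either time point. On that reading 20 participants do bring 20 lesions, and the remark about not controlling biopsy may refer only to additional lesions. The text leaves both readings open.

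Nor does any shortfall underpower the test: exact power at 18 and 19 lesions is above that at 20. Much of the gap between 90% and 80% reflects the choice of test, which 10.3 does not name.

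On bias, it can be said that the word known already means known before the scan, and that the study is a feasibility pilot that only estimates sensitivity. The first is a possible reading, but 10.3 does not define the term, and follow-up biopsies are collected for 12 months with no stated role that excludes them. The second limits the consequence of low power. It does not help with bias, which affects an estimate as much as a test.

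**Conclusion.** The concern holds in limited form. The count of 20 is asserted and not secured; the documents do not show that it will be missed. The loss of power becomes material at about 15 lesions: 64.8% exact, or 80.2% by the approximation that reproduces the plan's figure.

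Two further points stand whatever count is reached. RM2-directed biopsies are not kept out of the sensitivity denominator; 5 in 20 would add 7.5 points to a true 70% and raise the false-positive chance of the 15/20 rule about sevenfold (15.1/2.1). And 90% power at 20 lesions is a normal-approximation result, against 80.4% for an exact test that respects the 5% limit.

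These sizes rest on an assumed null of 50%, independent lesions, and an assumed 5 RM2-directed lesions. The protocol gives no basis for predicting that last number.

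**What to change.** Revise 10.3 as follows.

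- Define the sensitivity denominator as lesions that are biopsy-proven ER+, in place at the scan, and established independently of the 68Ga-RM2 result. This works on either reading of criterion 2.
- Report RM2-directed biopsies, and participants with no qualifying lesion, descriptively and outside the sensitivity estimate.
- Replace the assertion of at least 20 lesions with an expected count and the lesions per participant it assumes. Enrolment stays at 20.
- Name the test and the null value, and restate power over a range of counts. With a null of 50% and sensitivity of 80%, the exact one-sided 5% test gives 80.4% at 20 lesions, 79.8% at 16, 64.8% at 15 and 55.8% at 12 (normal approximation 90.3%, 82.7%, 80.2% and 70.6%). Note that a loss of one or two lesions matters little.

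The cost is wording, plus recording at chart review why each lesion was biopsied so that the rule can be applied. The stated power will look less favourable and the denominator may be smaller: excluding 5 of 20 lesions leaves 15. No scan, biopsy or eligibility criterion changes.
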